9.4.2 Disability Progression

Disability progression on the EDSS + indicates clinically significant worsening on at least 1 of the components of the EDSS + (EDSS, T25FW, 9HPT [either hand]) as defined by the clinically significant change thresholds in Section 4.3.1.) This will be based on the imputed dataset described in Section 9.3.1.

Progression on the EDSS + and each of its components will be analyzed by time point based on the criteria in Section 4.3.1. No confirmation will be required, i.e., progression at the analysis time point only is required.

The analysis will be presented at each time point with the number and percentage of subjects, and the 95% confidence interval for the proportion of subjects based on Wald confidence limits, and the odds ratio and corresponding 95% confidence interval based on the logistic regression model including baseline as a covariate and treatment as a main effect.

9.4.3 T25FW

The change from baseline in the T25FW during the Treatment Period will be analyzed using an MMRM. In addition to the summaries noted in Section 9.1, the pooled standard deviation, effect size, and 95% confidence interval of the effect size will be noted.

9.4.4 9HPT

The change from baseline in the 9HPT-D and 9HPT-ND during the Treatment Period will be analyzed using an MMRM. In addition to the summaries noted in Section 9.1, the

pooled standard deviation, effect size, and 95% confidence interval of the effect size will be noted.

9.4.5 Exploratory Patient and Clinician Measured Scales

The change from baseline in the total score for the MSIS-29, the total score for the BAC - Tower of London, the total score for the BAC – Verbal Memory, BAC - Tower of London T-score, BAC - Verbal Memory T-score, and the overall symptom score and most bothersome symptom score for the MSIOA will be analyzed at the collected time points using an MMRM.

9.4.6 SDMT

The change from baseline for the SDMT total score will be summarized based on the mITT analysis set using an MMRM.

The above analysis of change from baseline will be repeated for the subset of subjects with an SDMT total score < 50 at baseline using the same MMRM as described in the previous paragraph. The posterior probability of the difference of the group means being greater than 1 based on the SDMT total score will be presented. A non-informative prior will be used.

The number and percentage of subjects with a change from baseline in the SDMT total score ≥ 4 will be analyzed as observed. The analysis will be presented at each time point with the number and percentage of subjects, difference from placebo in responder rate, and the 95% confidence interval for the difference in proportion of subjects based on Wald confidence limits, and the odds ratio and corresponding 95% confidence interval based on the logistic regression model including baseline as a covariate and treatment as a main effect.

9.4.7 MFIS-5

The change from baseline for the MFIS-5 total score will be summarized based on the mITT analysis set using an MMRM.

The above analysis of change from baseline will be repeated for the subset of subjects with an MFIS-5 total score of ≥ 9 at baseline using the same MMRM as described in the previous paragraph. The posterior probability of the difference of the group means being greater than 1 based on the MFIS-5 total score will be presented. A non-informative prior will be used.

9.4.8 Low Contrast Visual Acuity

The change from baseline in low contrast visual acuity variables will be summarized as observed at each time point for the following parameters:

- Number of characters read, bilateral, 100% contrast level
- Number of characters read, bilateral, 2.5% contrast level
- Number of characters read, bilateral, 1.25% contrast level
- Number of characters read, right eye, 100% contrast level
- Number of characters read, right eye, 2.5% contrast level
- Number of characters read, right eye, 1.25% contrast level
- Number of characters read, left eye, 100% contrast level
- Number of characters read, left eye, 2.5% contrast level
- Number of characters read, left eye, 1.25% contrast level

The number of observations, mean, standard deviation, median, min and max will be presented.

The change from baseline in the number of characters read, bilateral at the 1.25% contrast level, will be summarized using an MMRM based on the population of subjects with a baseline deficit, defined as ≤ 11 characters (bilateral at the 1.25% contrast level) at baseline. The posterior probability that the mean difference between groups is > 2 using a non-informative prior will be calculated.

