3.7 Exploratory Endpoints

- 1. Disability improvement response rate on the T25FW, 9HPT, either hand, and EDSS at Weeks 12, 24, 36, and 52, and the EDSS + at Weeks 12, 24, and 36.
- 2. Change from Baseline on the T25FW and 9HPT, either hand, at Weeks 12, 24, 36, and 52
- 3. Disability progression response rate on the EDSS+ (T25FW, 9HPT, either hand, EDSS) and for each EDSS + component
- 4. 12- and 24-week confirmed disability improvement response rate on the EDSS + (T25FW, 9HPT, either hand, EDSS) and for each EDSS + component
- 5. Change from Baseline on the MS Impact Scale (MSIS-29) version 2 at Weeks 12, 24, 36, and 52
- 6. Change from Baseline on the Modified Fatigue Impact Scale (MFIS) at Weeks 12, 24, 36, and 52
- 7. Change from Baseline on cognition battery at Weeks 12, 24, 36, and 52:
 - Symbol Digit Modalities Test (SDMT) Oral Version
 - Brief Assessment of Cognition Verbal Memory Immediate Recall BAC App Version

- Brief Assessment of Cognition Tower of London BAC App Version
- Change from Baseline on the Low Contrast Visual Acuity (LCVA) assessments at Weeks 12, 24, 36, and 52
- 9. Change from Baseline in plasma biomarkers at Weeks 12, 24, 36, and 52
- 10. Change from Baseline on the MS Individualized Outcome Assessment (Multiple Sclerosis Individualized Outcome Assessment [MSIOA]) scale at Weeks 24 and 52
- 11. Change from Baseline in one week average daily step count and other activity measures (via home actigraphy with wearable biosensor) initiated at Weeks 24, 36, and 52

MRI Endpoints

The following imaging tests will be conducted. Details will be provided in the Statistical Analysis Plan (SAP).

- Lesion counts and volumes
- Brain and spinal cord atrophy measures
- Magnetization transfer ratio (MTR)
- Diffusion tensor imaging (DTI)

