7.3 Statistical Analyses for Efficacy

The ORS scores will be summarized descriptively (including n, mean, standard deviation, minimum, median, and maximum) along with the 95% confidence interval at each visit. The frequency and percentage of ORS for –4 to +4 will also be provided by treatment group at each visit. The ORS for each treatment group at scheduled visits and overall will also be estimated using a mixed-effect model for repeated measures (MMRM) including treatment group, visit, treatment-by-visit interaction, and stratification factors as fixed effects, with the baseline values for the ORS components as covariates.

For other continuous efficacy endpoints, the mean, standard deviation, median, minimum and maximum will be reported for each treatment group. The treatment comparison will be conducted using MMRM model including treatment group, visit, treatment-by-visit interaction, and stratification factors as fixed effects and the baseline value associated with the endpoint as a covariate.

For binary efficacy endpoints, the frequency and percentage will be provided by treatment group. The treatment comparison will be conducted using a logistic regression model adjusted for the stratification factors and baseline score associated with the endpoint.

All efficacy endpoints will be analyzed on mITT population. The RF and MMIA Sets will be used for the primary and other efficacy analyses as specified in the SAP.

Sample Size Estimation

Approximately 165 subjects will be equally randomized 1:1:1 (55 subjects in each treatment group, with a target of 20 SPMS subjects and approximately 35 RRMS subjects per treatment group). There are limited prior data to estimate the magnitude of effect and variance for a neurorestorative therapy. The sample size was therefore selected based on operational feasibility, variance seen in prior MS trials, and the likelihood of predicting success in subsequent phases of development.

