9.0 Efficacy Analyses

9.1 General Considerations

All efficacy endpoints will be analyzed on mITT analysis set. The primary and secondary efficacy endpoint analyses will be repeated for the RF analysis set and the MMIA set as described in Section 5.1. Additional exploratory analyses will be repeated based on a subset of the population with a pre-defined deficit at baseline where noted.

For all exploratory efficacy analyses other than those related to MRI variables, where a continuous summary by visit is noted, the descriptive statistics based on the observed visit values will be provided by treatment group. The statistics include number of observations, mean, standard deviation, minimum, median, and maximum. The number and percentage will be summarized for categorical variables.

For all efficacy endpoints where change from baseline will be analyzed with an MMRM, the mean at baseline and that visit will be presented, as well as the LS means standard error, and the between group difference, standard error, and 95% confidence interval.

Baseline for efficacy will be defined as the last non-missing observation that is on or before the first dose date.

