9.4 Other Efficacy Analyses

Change from baseline treatment comparison at each visit will be conducted using an MMRM model including treatment group, visit, treatment-by-visit interaction, and stratification factors as fixed effects, the baseline values associated with the endpoint as covariates. The REPEATED statement will be used for visit with blocks in the covariance matrix identified by subject nested within treatment group. The unstructured covariance structure will be used to estimate the within subject variance-covariance. If the model fails to converge, the first order autoregressive (AR[1]) covariance structure will be substituted. If the model still fails to converge, the compound symmetry (CS) covariance structure will be substituted. Denominator degrees of freedom will be computed using the Kenward-Roger method.

For binary efficacy endpoints, the frequency and percentage will be provided by treatment group unless otherwise noted.

9.4.1**Confirmed Improvement on the EDSS + and its components**

Confirmed 12-week disability improvement on the EDSS + or components of the EDSS + indicates a subject has clinically significant improvement at a visit as well as the next visit for one or more EDSS+ components, or if the next visit is missing, the subsequent visit. Confirmation may include assessments collected in the post-treatment follow-up period. The improvement confirmation must be in the same component of the EDSS +. If a subject has improvement in more than one component of the EDSS +, the subject must have confirmation in at least one of the same components to be considered as having confirmed disability improvement. For example, if a subject has clinically significant improvement in the T25FW at Week 12, the subject must have clinically significant improvement in the same component of the EDSS + at Week 24 (or if Week 24 is missing, Week 36) to be considered to have confirmed improvement.

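### SAP 9.4.8 models low contrast visual acuity only in a baseline-deficit subset on one chart, leaving the mITT endpoint with descriptive statistics only, contrary to the plan's general rules

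*SAP*

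**What the plan says.** **Endpoint.** Protocol 3.7 lists "Change from Baseline on the Low Contrast Visual Acuity (LCVA) assessments at Weeks 12, 24, 36, and 52". SAP 4.3.3 defines it the same way. Neither limits it to subjects with a visual deficit.

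**General rules.** For continuous efficacy endpoints other than the ORS, Protocol 7.3 says "The treatment comparison will be conducted using MMRM model including treatment group, visit, treatment-by-visit interaction, and stratification factors as fixed effects". On population it says "All efficacy endpoints will be analyzed on mITT population". SAP 9.1 agrees: "All efficacy endpoints will be analyzed on mITT analysis set". SAP 9.1 also gives the role of deficit subsets: "Additional exploratory analyses will be repeated based on a subset of the population with a pre-defined deficit at baseline where noted". SAP 9.4, which introduces all the other efficacy analyses, says "Change from baseline treatment comparison at each visit will be conducted using an MMRM model including treatment group, visit, treatment-by-visit interaction". SAP 4.7 makes the MMRM the default for continuous efficacy variables but lets a specific provision override it.

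**LCVA section.** SAP 9.4.8 provides two analyses:
- "The change from baseline in low contrast visual acuity variables will be summarized as observed at each time point for the following parameters". Nine parameters follow (bilateral, right eye and left eye, each at 100%, 2.5% and 1.25% contrast), with n, mean, SD, median, minimum and maximum.
- A model for the bilateral 1.25% parameter only, which "will be summarized using an MMRM based on the population of subjects with a baseline deficit". The deficit is 11 or fewer characters on that same chart. A posterior probability of a mean difference above 2 is added.

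**The concern.** The general text promises a modelled between-arm comparison of LCVA change in the mITT set, with the deficit subset as a second look. The LCVA section supplies the second look without the first. A programmer who follows SAP 9.4.8 would produce no adjusted difference, and no confidence interval for a difference, in the population for which the endpoint is defined. The 2.5% chart would have no modelled comparison in any population.

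Missing data add to this. In the Operations Manual visit tables, LCVA is marked as not needed when a Week 12, 24, 36 or 52 visit is held by phone, whereas MSIS-29 and MFIS-5 can be collected by phone. Operations Manual 3.6 gives EDSS, 9HPT and T25FW priority on return to site, with exploratory measures following if time allows. LCVA is therefore more exposed to pandemic-related gaps than MFIS-5. Yet MFIS-5 has a model on mITT that relies on missing at random, while LCVA on mITT has only means of whoever was tested at that visit.

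**Working it through.** **1. The scales side by side**

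| Section | Model on mITT | Model in deficit subset |
|---|---|---|
| SAP 9.4.6 SDMT | MMRM | Same MMRM, baseline score < 50 |
| SAP 9.4.7 MFIS-5 | MMRM | Same MMRM, baseline score ≥ 9 |
| SAP 9.4.8 LCVA | None stated; descriptive, as observed | MMRM, ≤ 11 characters, bilateral 1.25% only |

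SAP 9.4.5 also gives MSIS-29, the BAC scores and MSIOA an MMRM with no deficit restriction. LCVA is the only one of these scales whose sole model is confined to a subset. No reason is given.

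**2. The plan's own figure**

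No power or precision is stated for LCVA, so the trial's sample size serves as the reference. Inputs from SAP 4.4: 55 per arm, about 10% dropout, effect size 0.43, one-sided 0.10, t-test, about 80% power.

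Evaluable per arm = 55 × 0.9 = 49.5. The noncentral t calculation gives 80.2% power at 49.5 per arm and 80.5% at 50. The stated figure reproduces. I use n = 50 per arm below.

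**3. Precision in the subset**

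Let f be the share of subjects with a deficit. It is not in the documents, so a range is shown. With equal SD and f the same in each arm:

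- n in the subset = 50 × f per arm
- standard error of the difference = SD × sqrt(2/(50f)), which is the mITT standard error × 1/sqrt(f)
- 95% CI half-width = t(0.975, 2n − 2) × sqrt(2/n), in SD units

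| f | n per arm | 1/sqrt(f) | t × sqrt(2/n) | Half-width (SD) |
|---|---|---|---|---|
| 100% (mITT) | 50 | 1.00 | 1.984 × 0.200 | 0.40 |
| 70% | 35 | 1.20 | 1.995 × 0.239 | 0.48 |
| 50% | 25 | 1.41 | 2.011 × 0.283 | 0.57 |
| 30% | 15 | 1.83 | 2.048 × 0.365 | 0.75 |

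These are two-sample approximations at a single visit, not MMRM figures.

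**4. Power depends on who benefits**

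Both cases use one-sided 0.10, f = 50% and equal SD. The 0.43 is borrowed from SAP 4.4 and is not an LCVA value.

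- The same effect of 0.43 in every subject: 80% on mITT (n = 50) against 59% in the subset (n = 25).
- An effect of 0.43 in deficit subjects and none in the others: the mITT effect is 0.5 × 0.43 = 0.215. Power is about 42% on mITT against 59% in the subset.

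So the subset model can be weaker or stronger than the mITT model. Precision is always lower in the subset under the equal-SD assumption.

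**The case against.** The strongest reply is that the mITT comparison is already planned. SAP 9.4 states the change-from-baseline MMRM without exception and SAP 9.1 puts every efficacy endpoint on mITT. On that reading SAP 9.4.8 merely adds to the general rule. This stands in part: a reader might infer from SAP 9.4.8 that the plan rules out any mITT comparison of LCVA, and the documents as a whole do not support that. What they show is a specific section that departs from the general text. The reply does not remove the problem. SAP 4.7 allows a specific provision to displace the default, so SAP 9.4.8 can prevail, and the general text does not say which of the nine parameters would be modelled.

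Three further points stand:
- A reader might infer that subjects above the cut-off are lost. They are not. They remain in the as-observed tables, which SAP 9.1 gives by treatment group; only the model excludes them.
- A reader might infer bias because the subset is chosen on the baseline value of the same measure. The subset is defined before treatment and arms are compared as randomized. Regression to the mean would affect all arms alike.
- A reader might infer that the subset estimate inflates the treatment effect. That would need both an assumption that benefit is confined to deficit subjects and a reading of the result as a whole-population estimate. SAP 9.4.8 labels it as a deficit population.

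A deficit restriction also fits the trial's rationale. Protocol 4.2 says patients need disability for improvement to be detectable. This is a good reason to keep the subset analysis, but not a reason to leave out the analysis it is meant to repeat.

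**Conclusion.** The point holds as an inconsistency between the LCVA section and the plan's general rules. If SAP 9.4.8 is followed as written, an exploratory endpoint defined for all subjects has no adjusted, MAR-based between-arm estimate in its own population.

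The cost is scope and precision, not bias. The standard error is 1/sqrt(f) times that in mITT, and the 95% CI half-width rises from about 0.40 SD to 0.48, 0.57 and 0.75 SD at f of 70%, 50% and 30%. This rests on an assumed f, equal SD in the subset, about 50 evaluable subjects per arm and a two-sample approximation. No claim about lost power follows, because that depends on which subjects benefit.

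The stakes are low. LCVA is one of many exploratory endpoints in a Phase 2a trial without multiplicity adjustment (SAP 4.6), and no primary or secondary analysis depends on it. This is an inexpensive improvement rather than a serious flaw.

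**What to change.** In SAP 9.4.8, state that change from baseline in characters read, bilateral at 1.25% contrast, will be compared between arms on the mITT set with the section 9.4 MMRM, reporting LS means, difference and 95% CI. Keep the MMRM in subjects with 11 or fewer characters, and its posterior probability, as the repeat that SAP 9.1 describes. Bilateral 2.5% contrast could be modelled in the same way; this is optional, since the documents give that chart no special standing among the nine parameters.

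If mITT LCVA is meant to be descriptive only, SAP 9.4.8 should say so, give the reason, and record it as a departure from Protocol 7.3.

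The cost is a few lines of SAP text and one or two tables from a model already specified, with no new data. The downside is that some mITT subjects may read near the top of the chart, which could dilute a difference; the subset repeat addresses that.

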9.4.9 Actigraphy

Actigraphy was collected for 7 days starting at the visits at Week 0 (Baseline), 24, 36, and 52. The actigraphy parameters of movement including average gait cadence, moving duration, walking duration, number of steps and resting duration will be analyzed.

Moving duration, walking duration, number of steps, and resting duration will be normalized for the number of hours per day the subject is wearing the device, i.e., divided by the (device wear time duration [in seconds] \div 3600).

The analysis of change from Week 0 for each of the moving duration, walking duration, number of steps, and resting duration will be based on the average hourly value for that visit, i.e., the Week X value will be the sum of the daily average hourly values for that parameter divided by the number of days the subject wore a sensor within a window. The analysis of change from Week 0 for average gait cadence will be based on the average daily value of gait cadence for that visit, i.e., the Week X value will be the sum of the daily mean gait cadence values divided by the number of days the subject wore a sensor within a window. The pooled standard deviation, effect size, and 95% confidence interval of the effect size will also be noted.

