4 INVESTIGATIONAL PLAN

4.1 Overall Study Design and Plan

This is a 52-week, Phase 2a, proof-of concept, randomized, double-blinded, parallel-group, placebo-controlled multicenter study to evaluate the safety and efficacy of 2 doses of elezanumab in adult subjects with relapsing forms of MS who have established disability.

This study will include an approximate 30-day Screening period. The Treatment Period will include 14 visits from Baseline (Week 0) every 4 weeks through Week 52. Doses will be administered via Intravenous (IV) infusion at Week 0 (Baseline) and every 4 weeks thereafter through Week 48 for a total of 13 doses. The follow-up period includes 6 follow-up telephone calls that will occur at Weeks 56 through 76. All visits during the Treatment Period and Follow-up Period will be allowed a window of ± 7 days. Safety parameters such as clinical laboratory test results, ECG, and vital signs will be monitored (see Operations Manual [Appendix F]). Throughout the study and for a period of 39 weeks (5 half-lives) after the time of last study drug administration, females of childbearing potential will undergo monthly pregnancy testing; and for all subjects, AEs will be collected, whether solicited or spontaneously reported by the subject.

Eligible subjects will be randomized at the Week 0 - Baseline Visit to receive either elezanumab as an IV infusion or placebo in a 1:1:1 ratio (Section 5.8 and Section 7.3). Blinded doses will be administered intravenously every 4 weeks for 48 weeks. Subjects should remain on their current MS treatment regimen throughout the study.

During the Week 0 visit, subjects will be trained on the use of a wearable device. Subjects will be required to use the wearable device for 7 consecutive days at four time points (i.e., starting at the Week 0 visit and after visits at Weeks 24, 36, and 52), in countries where such devices are allowed.

Subjects who discontinue should complete the procedures outlined for the Early Discontinuation (ED) visit as soon as possible, preferably within 2 weeks (Section 5.5 and Section 5.6).

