3.14 Actigraphy

A wearable sensor will be used (when allowed per local regulatory guidelines) to enable data capture on actigraphy (activity, rest cycles) and daily step count. If regulatory approval in a participating country has not been received by the manufacturer, actigraphy data monitoring will not be done in that country. The actigraphy assessment will use BioStamp nPoint, which is a wireless remote monitoring platform intended for use by healthcare professionals and researchers for the continuous collection of physiological data in healthcare and home settings. BioStamp nPoint is designed to capture objective, real-world data from study subjects participating in clinical or academic studies and may be used wherever collection of relevant data is needed. BioStamp nPoint centers on body-worn BioStamp Sensors that can be worn for up to 24 hours at a time.

When BioStamp nPoint is used in the home or outside of the clinic ("Remote") setting, study subjects interact with the system through a Mobile Phone Application called the "Link App." The recharging and data transmission hub ("Link Hub") is used to recharge the sensors and synchronize data from the Sensors. The system is also capable of surface electromyography (sEMG) and monitoring limb and body movements during daily living and sleep. Training will be provided to site staff with instructions for subject use. Refer to Section 2 for the required administration times.

COVID-19 Pandemic-Related Acceptable Protocol Modifications

In the event this may not be performed due to study modifications related to the COVID-19 pandemic, actigraphy data will be captured at the next earliest feasible visit.

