4.3.3 Exploratory Efficacy Endpoints

The exploratory efficacy endpoints include:

- Disability improvement response rate on the EDSS, T25FW, 9HPT-D, and 9HPT-ND at Weeks 12, 24, 36, and 52, and the EDSS + at Weeks 12, 24, and 36.
- Change from Baseline on the T25FW, 9HPT-D, 9HPT-ND at Weeks 12, 24, 36, and 52
- Disability progression response rate on the Expanded Disability Status Scale Plus (EDSS +) (T25FW, 9-Hole Peg test [9HPT, either hand], EDSS) and for each EDSS + component

- 12- and 24-week confirmed disability improvement response rate on the EDSS + and for each EDSS + component
- Change from Baseline on the Multiple Sclerosis Impact Scale (MSIS-29) total score at Weeks 12, 24, 36, and 52
- Change from Baseline on the Modified Fatigue Impact Scale (MFIS) total score at Weeks 12, 24, 36, and 52
- Change from Baseline on cognition battery at Weeks 12, 24, 36, and 52:
 - Total score of the Symbol Digit Modalities Test (SDMT) – Oral Version
 - Total score and T-score of the Brief Assessment of Cognition Verbal Memory - Immediate Recall – BAC App Version
 - Total score and T-score of the Brief Assessment of Cognition Tower of London – BAC App Version
- Change from Baseline on the Low Contrast Visual Acuity (LCVA) assessments at Weeks 12, 24, 36, and 52
- Change from Baseline in select plasma biomarkers for monitoring target binding, neuroprotection and/or neurorestoration at Weeks 12, 24, 36, and 52
- Change from Baseline on the MS Individualized Outcome Assessment (MSIOA) scale overall symptom score and most bothersome symptom score at Weeks 24, and 52
- Change from Week 0 in average daily step count and other activity measures (as described in Section 9.4.3) via home actigraphy with wearable biosensor initiated at Weeks 24, 36, and 52
- Summary of variables from brain MRI at Baseline, Weeks 24 and 52
 - Presence of active T1 Gadolinium (GAD)-enhancing lesions
 - Presence of active new and enlarging T2 hyperintense lesions
 - Cumulative number of total T1 GAD-enhancing, lesions
 - Cumulative number of total T2 hyperintense lesions
 - Cumulative number of post-baseline T1 GAD-enhancing lesions
 - Cumulative number of post-baseline new and enlarging T2 lesions
 - Number of T1 GAD-enhancing lesions at each visit
 - Change from Baseline in total volumes of T1 GAD-enhancing, lesions

- Change from Baseline in total volume of T2 hyperintense lesions

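### SAP 9.4.9 averages gait cadence over all days of sensor wear, so any worn day without detected walking is counted as a cadence of zero

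*SAP*

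**What the plan says.** SAP 9.4.9 (Actigraphy) describes the collection as follows: "Actigraphy was collected for 7 days starting at the visits at Week 0 (Baseline), 24, 36, and 52". Protocol 4.1 agrees: "Subjects will be required to use the wearable device for 7 consecutive days at four time points".

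Five parameters are analysed. Four are adjusted for wear time: "Moving duration, walking duration, number of steps, and resting duration will be normalized for the number of hours per day the subject is wearing the" [sensor]. Their visit value is the "sum of the daily average hourly values for that parameter divided by the number of days the subject wore a sensor within a window".

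Cadence is handled separately and is not adjusted for wear hours. The aim is stated first: "The analysis of change from Week 0 for average gait cadence will be based on the average daily value of gait cadence for that visit". The SAP then spells this out as the "sum of the daily mean gait cadence values divided by the number of days the subject wore a sensor within a window". The denominator is therefore the same count of worn days that is used for steps and durations.

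SAP 9.4.9 gives no rule for a worn day that yields no cadence value. It does not set the day to missing, take it out of the denominator, or require a minimum amount of walking or wear. The endpoint is listed among the exploratory ones in SAP 4.3.3 as "Change from Week 0 in average daily step count and other activity measures"; cadence falls under the other measures.

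**The concern.** A count of worn days is a sound denominator for steps and walking duration, because a worn day without walking is a true zero for both. It does not suit cadence. Cadence is a rate during walking, and a day without walking has no cadence rather than a cadence of zero. The formula equals the average that the SAP says it wants only when every worn day has a cadence value.

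If some worn days have none, the weekly value becomes the mean cadence multiplied by the fraction of worn days with walking. Change from Week 0 would then mix two things: how the subject walks, and on how many days the subject walked. The second is already captured by steps and walking duration. The SAP reports a pooled standard deviation, an effect size and its confidence interval for these parameters, so the mixture would carry into reported results. Two programmers could also obtain different values, one following the formula and one averaging the non-missing days.

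**Working it through.** The documents give no figure for cadence, so there is no stated number to reproduce. The check is direct arithmetic on the formula.

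**Inputs**
- d: worn days in the window, up to 7 (SAP 9.4.9; Protocol 4.1).
- k: worn days without a cadence value. The documents do not give it, so it is varied.
- c: the subject's mean cadence over days with a value. It is set to 100 in arbitrary units as an assumption; the relative error does not depend on it.

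**Weekly value**
- Literal formula: the daily values sum to c(d − k), so the result is c(d − k)/d.
- Mean over days with a value: c(d − k)/(d − k) = c.
- Relative error: (d − k)/d − 1 = −k/d.

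This holds whether the day is left out of the sum or entered as 0, and whether or not the other daily values are equal.

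| Worn days d | k = 1: value (error) | k = 2: value (error) |
|---|---|---|
| 7 | 85.7 (−14.3%) | 71.4 (−28.6%) |
| 6 | 83.3 (−16.7%) | 66.7 (−33.3%) |
| 5 | 80.0 (−20.0%) | 60.0 (−40.0%) |
| 4 | 75.0 (−25.0%) | 50.0 (−50.0%) |
| 3 | 66.7 (−33.3%) | 33.3 (−66.7%) |

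**Change from Week 0**, with true cadence constant at c. Subscript 0 marks Week 0 and subscript 1 the later visit.
- Computed change = c(1 − k₁/d₁) − c(1 − k₀/d₀) = c(k₀/d₀ − k₁/d₁). The true change is 0.
- d = 7 at both visits, one such day at the later visit only: 100 × (0 − 1/7) = −14.3.
- One such day at Week 0 only: 100 × (1/7 − 0) = +14.3.
- One such day at each visit: 100 × (1/7 − 1/7) = 0.

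Equal shares therefore create no spurious change. A true change would only be scaled by the common factor, 6/7 in the last case.

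**Group level**

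Bias in the treatment contrast needs the average of k₀/d₀ − k₁/d₁ to differ between arms. The documents give nothing from which to estimate that.

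**The case against.** The strongest reply is that SAP 9.4.9 never mentions days without walking. The formula restates a daily average and equals it whenever every worn day has a value. A programmer might average the non-missing days as a matter of course. The SAP also refers (11.1, 12.1) to a statistical programming plan that is not among the documents and may or may not settle the matter. This stands as a limit: the plan does not say that such days are entered as zero. That follows from the literal denominator, and only if such days occur.

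It is also fair that such days may be uncommon. Operations Manual 2.1 asks that sensors be applied on the day of the timed walk at Week 0. The Activity Schedule (Protocol Appendix D) has the equipment worn at the visit and over the following week, with the T25FW scheduled at Weeks 0, 24, 36 and 52. The first wear day should therefore normally include walking. The top of the eligible EDSS range, 6.5, does not describe the typical subject. The Operations Manual 3.14 remark about "body-worn BioStamp Sensors that can be worn for up to 24 hours at a time" says nothing about walking.

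Two stronger readings are tempting, and the documents support neither.

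- A reader might infer that the trial's cadence results are biased by 14%. That figure is an error in one subject's weekly level when one of seven worn days lacks walking. It is neither an error in the treatment contrast nor, in general, in the change from Week 0.
- A reader might infer a large loss of precision. With level 100, seven worn days and independent days at one common probability p in every subject, the variance of change is multiplied by 1 + [2 × 100² × p(1 − p)/7]/SD². For p = 2%, 5% and 10%, an SD of change of 5.7 gives 2.7, 5.2 and 8.9; an SD of 15 gives about 1.2, 1.6 and 2.1. Neither p nor the SD is in the documents, and the factor would be smaller if such days cluster in a few subjects. No particular inflation can be claimed.

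**Conclusion.** The point holds as a minor defect in a stated rule. The written formula matches the SAP's own description of the quantity only if every worn day has a cadence value. Otherwise it understates the subject's weekly cadence by k/d, which is 14.3% for one of seven worn days, and it distorts change from Week 0 when the share of such days differs between the two weeks.

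This rests on two things: that the formula is programmed as written, and that some worn days have no detected walking. The documents do not establish how often the latter happens. Group-level bias and variance inflation therefore cannot be quantified, and the effect is nil if no such days occur. Cadence is one of five actigraphy parameters in an exploratory endpoint. It does not enter the ORS or the EDSS+, so the primary and secondary analyses are unaffected.

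**What to change.** In SAP 9.4.9, change the cadence denominator to the number of worn days in the window with a non-missing daily mean cadence. Add one sentence: a worn day without detected walking is missing for cadence but stays in the steps and walking-duration averages as zero. For seven worn days, one of them without walking, and a cadence of 100 on the other six, the weekly value is then 600/6 = 100 instead of 600/7 = 85.7.

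The cost is one phrase in the SAP and one line of code. The small downside is that a subject with no walking day at a visit has missing cadence there. If outputs already exist, confirm which denominator was used and say so in the report.
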